### **7.8. Baseline Physical Examination**

Physical examination findings, including baseline, will be listed.

### **7.9. Baseline Primary and Secondary Effectiveness Evaluations**

All attacks (subject-reported and adjusted) will be listed.

Similarly, a summary of baseline AE-QoL total and domain scores will be presented in an appropriate summary table.

## **8. EFFECTIVENESS**

### **8.1. General Considerations**

As the primary nature of this study is to evaluate the safety of BCX7353, effectiveness is considered of secondary importance. No formal testing will be conducted.

### **8.2. Subgroup Analyses**

Subgroup analyses for effectiveness endpoints will not be performed.

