5.4.3. Study Population Rationale

The study will be limited to adults and adolescents ≥ 12 years of age of both sexes. Children <12 years of age will be excluded from participation in BCX7353 clinical trials until the benefit-risk profile in adults and adolescents has been better characterized. Population PK modeling of PK data generated to date indicate that weight is a covariate on the bioavailability of BCX7353. Simulations of exposures by weight at clinically relevant doses indicated that a weight of < 40 kg is associated with exposures considered significantly higher (ie, $> 20\%$) than those generated from an adult of 70 kg at doses to be studied in this protocol. Therefore, participation in the trial will be restricted to subjects who weigh at least 40 kg. At a weight of 40 kg, simulated exposure was well within the efficacious exposures identified in Study BCX7353-203 that were well-tolerated; therefore, it is anticipated that exposure in adolescent subjects will not exceed safe and tolerable exposures in adults.

In the ongoing BCX7353-204 trial, asymptomatic and transient transaminase elevations have occurred almost exclusively in subjects who have recently (ie, < 2 weeks prior to starting BCX7353) discontinued androgens (BCX7353 IB). Currently the physiological and HAE attack changes that may occur with androgen cessation are not well described. Since androgen use (both current and past) is prevalent in the global HAE community, this protocol will provide data to better characterize androgen discontinuation in HAE patients and allow the development of guidance for treaters and patients who wish to switch from androgens to BCX7353. In order to reduce the incidence of transaminase elevations on study, subjects will be required to have last used androgens at least 28 days prior to initiation of BCX7353.

To date, the BCX7353-204 trial has been conducted primarily outside of the US, including many areas where use of long-term prophylaxis for HAE attacks is uncommon. Since use of prophylactic therapy for HAE attacks is prevalent in the US HAE community, this protocol will provide data to allow the development of guidance for treaters and patients who wish to switch from another prophylactic therapy to BCX7353.

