9.7. Concomitant Medications

All subjects in the study must refrain from taking prohibited concomitant medications as outlined in Section [9.7.1](#).

Details of all prior medications (taken within 30 days of screening) and all current concomitant medication use (including herbal supplements), including all medications administered for the treatment of AEs, will be recorded in the source documentation /CRFs.

Subjects whose illness is being treated with C1-INH, tranexamic acid, or lanadelumab prophylaxis regimens are allowed to continue on their regimen; however, the Investigator is encouraged to assess response to BCX7353 therapy and reduce and/or discontinue prophylactic C1-INH, tranexamic acid, or lanadelumab use over time if clinically warranted.

Steady state levels of BCX7353 are reached with daily dosing between 6 and 12 days. Therefore, the following strategies are recommended for subjects who are beginning BCX7353 in place of another method of prophylaxis:

Table 2. Recommended Strategies for Switching to BCX7353 Prophylaxis from Another Therapy

Current Prophylactic Therapy	Timing of BCX7353 Initiation
Androgens (eg, danazol)	Discontinue androgens. Day 1 of BCX7353 dosing may occur a minimum of 28 days after the last dose of androgens. Androgens may be discontinued or tapered in accordance with the usual practice of the Investigator; however, last dose must occur a minimum of 28 days prior to BCX7353 initiation.
Tranexamic acid	Discontinue tranexamic acid dosing 14 days after first dose of BCX7353.
C1-INH (eg, Cinryze, Haegarda)	Discontinue existing C1-INH dosing schedule 14 days after first dose of BCX7353.
Lanadelumab-flyo	Day 1 of BCX7353 dosing to occur on same day as lanadelumab injection. No further dosing of lanadelumab is required after initiating BCX7353.

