13. STATISTICS

13.1. Sample Size Considerations

No sample size calculations were conducted for this open-label, long-term safety study. Approximately 475 subjects may be enrolled in this study, with approximately 250 subjects planned to be enrolled in the US, to provide access to BCX7353 for additional subjects who, in the opinion of the Investigator, are expected to benefit from treatment with an oral treatment for the prevention of angioedema attacks.

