13.3.6. Analysis of Effectiveness Variables

The following effectiveness endpoints will be summarized and listed by treatment group:

- Number and rate of HAE attacks
- Durability of response
- Number and proportion of days with angioedema symptoms days
- Patient-reported outcomes: HAE disease-specific AE-QoL questionnaire scores and TSQM Global Satisfaction scores
- Number of attacks requiring attack medication
- Discontinuations due to lack of efficacy (through 48 weeks only)
- Disease severity

All attacks recorded by the subjects will be reviewed and confirmed or rejected according to a set of pre-defined rules prior to inclusion in effectiveness analyses. These rules, which will be constructed in concert with HAE-treating physicians, will be outlined in the SAP.

The attack rate will be calculated as the number of attacks per month (28 days) by treatment for each subject, adjusted for the total duration of treatment. The attack rate will be listed and summarized using all available data. The durability of response assessment will be based on attack rate trend over time. Alternatively, the attack rate change may also be assessed relative to recent HAE attack documentation. Summaries and/or comparisons of effectiveness endpoints may be performed for those who received concomitant C1-INH and those who did not.

Additional related details of HAE attacks (e.g., hospitalizations and emergency room visits) and number of days lost from work and/or school due to attacks will be summarized and listed. Summaries may be produced separately for pre-96 week attacks and post-96 week attacks as fewer details are collected in the diary post 96 weeks.

Details of these analyses will be provided in the SAP.

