## **11. CHANGES FROM PROTOCOL-SPECIFIED ANALYSES**

Changes from protocol-specified analyses include: removal of the intent-to-treat population, removal of analysis of disease severity, removal of comparison of effectiveness endpoints between subjects who received the indicated dose and a reduced dose, removal of comparison of effectiveness endpoints for those that received concomitant C1-INH and those who did not.

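### No planned effectiveness analysis separates time on BCX7353 alone from time on BCX7353 plus another prophylactic, so attack control after a switch will not be reported

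*SAP*

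**What the plan says.** **Purpose.** Protocol 5.4.3 notes that prophylaxis is common among US patients and says that "this protocol will provide data to allow the development of guidance for treaters and patients who wish to switch from another prophylactic therapy to BCX7353".

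**What subjects may take.** Under Protocol 9.7, subjects on C1-INH, tranexamic acid or lanadelumab "prophylaxis regimens are allowed to continue on their regimen". The investigator is encouraged to reduce or stop the other drug if clinically warranted, with no fixed end date. Protocol Table 2 adds recommended timings for those replacing another drug. For C1-INH it reads "Discontinue existing C1-INH dosing schedule 14 days after first dose of BCX7353"; tranexamic acid has the same 14 days; for lanadelumab no further dosing is required once BCX7353 starts.

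**What will be analysed.** SAP 6.7.8.3 divides attacks by the length of the whole reporting period. SAP 8.3.1.1 presents the adjusted rate by month and for the entire dosing period, by treatment group. SAP 8.2 then says "Subgroup analyses for effectiveness endpoints will not be performed". Protocol 13.3.6 had left an option open: "Summaries and/or comparisons of effectiveness endpoints may be performed for those who received concomitant C1-INH and those who did not". SAP 11 lists among its changes the "removal of comparison of effectiveness endpoints for those that received concomitant C1-INH and those who did not". SAP 6.6.1 calculates no baseline attack rate, partly because some subjects are on other prophylactics.

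**What remains for these subjects.** SAP 7.7 summarises those entering on prophylaxis and estimates time to stopping it by Kaplan-Meier. SAP 9.3.1 gives one summary of treatment-emergent adverse events during simultaneous use. Medications and attacks are listed.

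**The concern.** A reader of the attack-rate tables will want to know what happens to attacks on BCX7353 alone, and in particular after the earlier prophylactic is stopped. The planned tables cannot answer either question. Days on two prophylactics and days on one enter the same numerator and denominator, and subjects who never used prophylaxis are mixed with those who switched. With no baseline rate there is no pre-switch reference either.

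Two things are at stake. One is a gap between a stated rationale and the planned outputs: time to stopping prophylaxis and adverse events during overlap describe a switch, but say nothing about attack control after it. The other is interpretation of the pooled rate. SAP 6.7.8.5 defines durability of response as the trend in monthly adjusted attack rates, and a short overlap falls entirely in the first month of that trend.

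**Working it through.** **1. The plan's own figures.** There is no power calculation to reproduce: "No sample size calculations were conducted for this open-label, long-term safety study". The formula that matters is in SAP 6.7.8.3: rate = attacks × 28 / days in the reporting period. Its example of 2 attacks in 14 days gives 2 × 28 / 14 = 4 per month, as stated. Nothing in the numerator or denominator depends on concomitant prophylaxis, so pooling is confirmed.

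**2. Effect on the pooled mean.** Let p be the share of subjects entering on another prophylactic, f the share of their time on both drugs, and r_alone and r_both the two rates. With equal follow-up and the same underlying disease in both groups,

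pooled rate = r_alone − p × f × (r_alone − r_both).

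Inputs:
- r_alone = 1.31 attacks per 28 days, the 150 mg rate in Study BCX7353-302 Part 1 (Protocol 5.2.1), used for illustration only.
- r_both = 0.3 to 1.0 and p = 20% to 60%. These are assumptions; the documents give neither.
- f from the timings: 14/672 = 2.1% of 96 weeks, or 14/28 = 50% of Month 1, for a 14-day overlap (Protocol Table 2); 50% or 100% if prophylaxis continues for half or all of dosing.

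The smallest shift uses p = 0.2 and r_both = 1.0 (gap 0.31). The largest uses p = 0.6 and r_both = 0.3 (gap 1.01).

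| Scenario | f | Smallest shift | Largest shift | Pooled rate | Relative to 1.31 |
|---|---|---|---|---|---|
| 14-day overlap, 96 weeks | 0.021 | 0.2 × 0.021 × 0.31 = 0.001 | 0.6 × 0.021 × 1.01 = 0.013 | 1.30–1.31 | 0.1–1.0% |
| 14-day overlap, Month 1 | 0.50 | 0.2 × 0.50 × 0.31 = 0.031 | 0.6 × 0.50 × 1.01 = 0.303 | 1.01–1.28 | 2–23% |
| Continued for half of dosing | 0.50 | 0.031 | 0.303 | 1.01–1.28 | 2–23% |
| Never stopped | 1.00 | 0.2 × 0.31 = 0.062 | 0.6 × 1.01 = 0.606 | 0.70–1.25 | 5–46% |

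If every subject overlapped for 14 days and the other drug cut the rate by 50–80%, the 96-week effect would be 2.1% × 0.50 to 2.1% × 0.80, or 1.0–1.7%.

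For durability, Month 1 at 1.01–1.28 followed by Month 2 at 1.31 would look like a rise of 0.03 to 0.30 with no change in the effect of BCX7353.

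**3. Direction.** The sign rests on r_both being below r_alone. Protocol 5.4.4 and 9.7 tie tapering to response, so those who stay on two drugs may have more active disease. If their rate on both drugs were 2.0 (assumed), with p = 0.4 and f = 1, the pooled rate would be 1.31 + 0.4 × 0.69 = 1.59, above rather than below 1.31.

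**4. Precision of a split.** With SD 1.40 (Month 1, 150 mg, subjects treated through Week 48; Protocol 5.2.2), the 95% half-width is 1.96 × 1.40 / √n: 0.55 attacks per month for n = 25, 0.39 for n = 50 and 0.27 for n = 100.

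**The case against.** The case against is substantial, and much of it stands.

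- **A reader might infer that the trial cannot inform switching at all.** The documents do not support that. Time to stopping prophylaxis, adverse events during overlap, and listings of attacks and medications are all planned. Protocol 5.4.3 promises data from which guidance could be developed, not a named analysis. The gap is in the planned effectiveness outputs, not in what is collected.
- **A reader might infer that the pooled rate necessarily flatters BCX7353.** Continuation depends on response, so the direction is not established (step 3).
- **A reader might infer that the US cohort was sized or enrolled for switching.** Protocol 13.1 gives access to treatment as the reason for the numbers, Protocol 5.4.1 adds long-term safety and effectiveness in US subjects, and switching is not among the objectives in Protocol 6.1.
- **A reader might infer that a committed analysis was withdrawn.** Protocol 13.3.6 is permissive, and the SAP discloses the omission.
- **Monthly rates help in part.** For subjects who follow Table 2 for C1-INH or tranexamic acid, Month 2 onward is post-switch time. But those months are pooled with subjects who never used prophylaxis and with those who continued it, so the post-switch rate is not visible.
- **The SAP predates the current protocol.** SAP Table 2 stops at protocol version 5.0, and the SAP plans about 225 subjects in two dose groups. The protocol refers to versions up to 9.0 and about 475 subjects. No later SAP is supplied, so the SAP 8.2 prohibition may not govern the final analysis. This bears on when to make the change; it does not remove the need for it.
- **Effectiveness is secondary and untested (SAP 8.1).** That limits the weight of the point, but a descriptive split needs no test.

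**Conclusion.** The point holds in a limited form. No planned effectiveness analysis in the supplied SAP separates BCX7353-alone time from combined time, and none shows attacks after a switch, although Protocol 5.4.3 presents switching data as something the study will provide.

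The documents do not state the effect on the pooled rate. Under the assumed prophylaxis shares and rates it is about 1–2% or less of the 96-week rate with a 14-day overlap, which is negligible. It could reach about 0.3 attacks per month in Month 1, and about 0.6 if prophylaxis never stops. These figures assume equal underlying disease in users and non-users; without that assumption even the sign is open. The primary safety objective is untouched. This is a cheap improvement that should be made, not a flaw that invalidates the analysis.

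**What to change.** When the SAP is updated to the current protocol:

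1. Replace the SAP 8.2 prohibition with a descriptive summary of adjusted attack rates, overall and by month (Tables 14.2.1.1 and 14.2.1.8.1), by prophylaxis at entry: none, C1-INH, lanadelumab, tranexamic acid. Amend SAP 11 to match.
2. Add lanadelumab to the SAP 6.7.5 definition of entering on prophylaxis. It now lists only C1-INH products and daily tranexamic acid, so the lanadelumab group cannot be formed and these subjects may also be missed in the SAP 7.7 and 9.3.1 outputs. Do not form the groups from the C1-INH grouping in SAP 7.6, which also contains lanadelumab, icatibant and ecallantide.
3. As a supplement, show rates for on- and off-prophylaxis person-time, with a stated analysis rule for when on-time ends after the last dose. Label this split as non-randomised, because stopping depends on response and off-time may therefore be weighted towards good responders.

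If a later SAP already exists, the sponsor should confirm that it contains such a split.

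Cost: a few descriptive tables from data already collected, with no new assessments or tests. Downsides are small cells (half-width about 0.55 attacks per month at n = 25 with SD 1.40), a possibly less favourable BCX7353-alone rate, and selection in the on/off split. The change concerns analysis only and implies nothing about how prophylaxis should be managed.

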### **8.3. Analysis of the Effectiveness Endpoints**

#### **8.3.1. Effectiveness Analysis**

The effectiveness analysis is comprised of multiple endpoints (Section 3.2.2) and will be conducted on the safety population.

##### **8.3.1.1. HAE Attack Rate**

The number of subject-reported and adjusted HAE attacks will be analyzed by treatment group using appropriate descriptive statistics. The adjusted attack rate (expressed as attacks/month) will be presented by month as well as for the entire study dosing period.

##### **8.3.1.2. Number and Proportion of Days with Angioedema Symptoms**

The number and proportion of days with angioedema symptoms reported from adjusted attacks will be summarized by month as well as for the entire study dosing period using descriptive statistics by treatment group.

##### **8.3.1.3. Number and Proportion of Subjects Attack Free**

The number and proportion of subjects adjusted attack free will be summarized using descriptive statistics by treatment group.

##### **8.3.1.4. Discontinuations Due to Lack of Efficacy**

The number of subjects who discontinue due to lack of efficacy will be provided with subject disposition and will be summarized by treatment group.

##### **8.3.1.5. Attack Characteristics**

Characteristics of adjusted attacks, including location of attack, duration of attacks from start to finish and from start to the time the worst symptoms of the attack were over, triggers, swelling, other symptoms, whether the attack was treated, severity as assessed by the subject's ability to do daily activities, appearance affected, professional care sought, and location of professional care will be summarized and listed.

The time to first adjusted attack will be estimated using Kaplan-Meier. Subjects who do not experience an adjusted attack will be censored at the time of study treatment discontinuation.

A summary of duration of attack for abdominal, peripheral, and mixed attacks will also be provided for subject-reported and adjusted HAE attacks.

#### **8.3.1.6. Use of HAE Attack Medications**

Use of HAE medications as noted in the diary will be summarized separately from concomitant medications as noted in Section 7.7. In addition, summaries of the number of subject-reported HAE attacks requiring treatment will be provided.

The time to first use of HAE targeted rescue medication for an adjusted attack will be estimated using Kaplan-Meier estimates. Subjects who do not use HAE rescue medication will be censored at the time of study treatment discontinuation.

#### **8.3.1.7. AE-QoL**

Subject-reported outcomes including the AE-QoL questionnaire domain scores (total, functioning, fatigue/mood, fears/shame, and nutrition) will be calculated as discussed in Section 6.7.8.14. The AE-QoL will be summarized by domain/subscale, visit and treatment group using descriptive statistics.

#### **8.3.1.8. TSQM**

TSQM is measured at baseline and represents satisfaction with their usual medication. The baseline scores may be reflective of satisfaction with the subject's previous treatment or with no treatment.

TSQM scores for Effectiveness, Side Effects, Convenience, and Global Satisfaction and corresponding change from baseline values will be calculated for each visit as discussed in Section 6.7.8.15. The TSQM scores will be summarized by score, treatment and visit.

## **9. SAFETY AND TOLERABILITY**

### **9.1. Overall Summary of Tolerability**

The summaries of tolerability will be presented in the tables described in Section 9.3 and Section 9.4.

### **9.2. Subgroup Analyses**

The following subgroup analyses for selected safety endpoints will be performed:

- Prior androgen use (latency: time between stopping androgen and starting BCX7353: < 2 weeks, 2 weeks to < 1 month, 1 month to < 2 months, and  $\geq$  2 months)
- Duration of prior androgen use (never used, < 6 month, 6 months to < 1 year, 1 year to < 5 years, 5 years to < 10 years,  $\geq$  10 years).

### **9.3. Adverse Event Preferred Term and Body/Organ System Summary Tables**

The following are safety endpoints:

- Proportion of subjects with TEAEs
- Proportion of subjects with TESAEs
- Proportion of subjects who discontinue BCX7353 due to a TEAE
- Proportion of subjects with treatment-emergent Grade 3 or 4 AEs
- Proportion of subjects with treatment-emergent, treatment-related AE consistent with a drug rash
- Proportion of subjects with treatment-emergent Grade 3 or 4 laboratory abnormalities

AEs will be mapped to a MedDRA version 19.1 SOC and PT. If a subject experiences multiple events that map to a single preferred term, the greatest severity grade according to the Division of Microbiology and Infectious Diseases (DMID) November 2007 criteria and strongest investigator assessment of relation to study medication will be assigned to the preferred term for the appropriate summaries. Should an event have a missing severity or relationship, it will be classified as having the highest severity and/or strongest relationship to study medication. All AEs will be listed for individual subjects showing both verbatim and preferred terms.

TEAEs are defined as AEs that occurred on or after first dose of study treatment through 30 days post-discontinuation of study treatment. All AEs that occurred prior to the initiation of study treatment or those recorded after 30 days after the last dose of study treatment will be excluded from the tables but will be included in the listings.

Drug-related events are defined as those AEs that the Investigator believes were possibly, probably, or definitely related to the study drug.

#### **9.3.1. Summaries of Adverse Event Incidence Rates for All Subjects and Adverse Incidence Rates for Serious Adverse Events, Adverse Event Dropouts, and Death**

A brief summary of AEs will show, by treatment group, the number and percentage of subjects who 1) had any AE, 2) had any drug-related event, 3) permanently discontinued from study drug due to an AE, 4) had any serious adverse event (SAE), 5) had any Grade 3 or higher AE, 6) had any Grade 3 or higher drug-related AE, 7) had any AE leading to interruption of study drug, 8) had a drug-related SAE, or 9) had a fatal SAE.

AEs will be summarized by treatment group. For each SOC and PT, the number and percentage of subjects reporting an event will be calculated. In summary tables, SOC and events within a SOC will be presented by decreasing frequency count based on the total number of events. Multiple events (by subject or SOC as appropriate) will be counted only once per subject per dose in each summary. For summaries that use severity grade, the most severe event will be selected.

The following summary tables (number and percentage of subjects) of TEAEs (by SOC and PT) will be provided by treatment group:

- Overall summary of TEAEs
- Summary of TEAEs
- Summary of drug-related TEAEs
- Summary of treatment-emergent adverse events by severity
- Summary of Grade 3 or Grade 4 TEAEs
- Summary of drug-related, Grade 3 or Grade 4 TEAEs
- Summary of TESAEs
- Summary of TEAEs leading to permanent discontinuation of study treatment
- Summary of TEAEs leading to interruption of study treatment
- Summary of drug-related, TESAEs

In addition, summaries of frequent TEAEs and drug-related TEAEs will be provided by preferred term (not by SOC and PT), in decreasing order of frequency. Frequent TEAEs will be defined as TEAEs that occur in at least 5% of the total number of subjects in the clinical trial. The number of events will be displayed on all summary tables except the overall summary of TEAEs. All TEAE analyses will be repeated using subgroups.

A single presentation of the summary of TEAEs for subjects entering on prophylactic medications will be presented. For this presentation, only TEAEs occurring while the subject was simultaneously taking BCX7353 and prophylactic medication will be summarized.

Data listings will be provided for all AE data. In addition to listing all AEs, distinct data listings will also be provided for the following:

- Grade 3 or Grade 4 AEs
- AEs leading to permanent study discontinuation
- SAEs (fatal and non-fatal)

